**SUMMARY OF CHANGES**

**PRIMARY REASON(S) FOR THIS AMENDMENT:**

Section Number (s)	Section Title(s)	Description of Change (s)	Rationale
1.0 2.1 4.2.1.2 5.1.3 7.1.2.3.1	Trial Summary  Trial Design  Rationale for Trial and Selected Subject Population  Subject Exclusion Criteria  Confirmation of Progression to Probable AD Dementia	Eligibility criteria modified to exclude subjects who progress to dementia due to AD based on investigator diagnosis in the main 104 week study from entering the long term extension study.	Results of the Phase 2/3 clinical study MK-8931-017 did not show a benefit in AD patients who initiated MK-8931 treatment in the mild to moderate dementia stage. Therefore, the balance of benefit/risk no longer supports entry of subjects with AD dementia in the extension, where active treatment may be newly initiated. Regarding continued treatment of subjects who progress to dementia later in the trial, it is not known whether initiation of treatment at the prodromal stage would provide benefit to these subjects. Therefore, despite the lack of efficacy in the 017 population of subjects with mild to moderate dementia, the sponsor believes that continued treatment of these subjects is warranted.

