## **2.0 TRIAL DESIGN**

### **2.1 Trial Design**

This is a long-term safety and efficacy study (up to 260 weeks) which will be available to subjects who have completed the initial 104-week trial of MK-8931-019.

The initial 104-week trial is a double blind, randomized, parallel group, placebo controlled, multicenter trial in subjects with amnesic mild cognitive impairment (aMCI) due to Alzheimer's Disease (AD), referred to herein as prodromal AD. The initial 104-week trial, detailed in a separate amendment, includes two active dose arms of MK-8931 (12 mg and 40 mg) and placebo. Duration of treatment is 104 weeks (24 months). MK-8931 is a potent  $\beta$ -site APP cleaving enzyme 1 (BACE1) inhibitor being developed for the treatment of AD. The initial 104-week trial will enroll subjects who meet criteria for prodromal AD, which is defined as subjects who have aMCI and are positive for an AD biomarker. The primary AD biomarker to be used for the inclusion criterion is cortical amyloid load measured with positron emission tomography (PET).

At the end of the 104-week trial, subjects who have completed treatment and satisfy eligibility criteria may choose to participate in this trial, during which all subjects who received placebo during the initial 104-week trial will receive active drug. Subjects who progress to dementia due to AD in the main 104 week study will not be permitted to move into the long term extension study.

This trial will start with enrollment of the first subject who completes the initial 104-week trial and chooses to participate in the long term trial. The long term safety and efficacy trial will end 5 years after the first subject enrolls (260 weeks), or a) when the drug either becomes commercially available (locally), or b) when the MK-8931 program is terminated (whichever comes first). The duration of the trial may be even shorter for subjects in particular regions, per local regulation.

Specific procedures to be performed during the trial, as well as their prescribed times and associated visit windows, are outlined in the Trial Flow Chart - Section 6.0. Details of each procedure are provided in Section 7.0 – Trial Procedures.

This trial will use an independent, external Data Monitoring Committee (eDMC) to monitor safety at the appropriate frequency and for the duration required per the eDMC Charter.

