#### **4.2.1.2 Rationale for Subject Population and Dose**

The recent results from Protocol 017 indicate that MK-8931 is not effective when treatment is initiated in subjects with mild/moderate AD. The amyloid hypothesis suggests, however, that earlier treatment with a BACE inhibitor (prior to the onset of dementia) could be beneficial even if ineffective at later stages. The initial 104-week trial of Protocol 019 in prodromal AD is still ongoing so the impact of BACE inhibition in this earlier stage of the disease is not yet known. Given this uncertainty along with the 017 results, subjects who tolerated study medication, have not progressed to dementia and completed the initial 104-week trial of Protocol 019 may enroll in this long term trial. However, subjects who have progressed to dementia will be excluded since the 017 results indicate increased adverse events in addition to no efficacy.

Subjects in the initial 104 week trial who progress to dementia during that time have a 2 out of 3 chance of being on active treatment with MK-8931. Based on the view that these subjects could still benefit from MK-8931 since it was initiated before the onset of dementia, one alternative is to allow these subjects into the extension trial. However, since the blind will be maintained in the extension, it is not possible to include these subjects while excluding subjects who were on placebo during the initial 104-week trial. Given the concern that the placebo treated subjects who progress to dementia would not benefit from treatment, the current protocol will exclude all subjects who have progressed to dementia.

Subjects who progress to dementia during this extension trial will be allowed to continue, since it is not known whether initiation of treatment at the prodromal stage would provide benefit to these subjects. Therefore, despite the lack of efficacy in the 017 population where treatment was initiated at the mild to moderate dementia stage, the sponsor believes that continued treatment of these subjects is warranted.

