### **5.1.3 Subject Exclusion Criteria**

The subject must be excluded from participating in the trial if the subject:

1. Has progressed to dementia due to AD per investigator diagnosis in the initial 104-week study.
2. Is in imminent risk of self harm, based on clinical interview or on the Columbia Suicidality Severity Rating Scale (C-SSRS), or of harm to others in the opinion of the investigator. Subjects who report suicidal ideation with intent, with or without a plan (e.g., suicidal ideation item 4 or 5 on the C-SSRS) in the past one (1) month or suicidal behavior in the past six (6) months should be excluded. Such subjects will be permitted to rescreen for entry into this study once in the Investigator's opinion, this risk of harm to self or others is no longer present.

3. Has developed a recent or ongoing, uncontrolled, clinically significant medical or psychiatric condition that precludes participation in this protocol in the judgment of the investigator.
4. Based on results from the EOT Visit (Visit 12) in the initial 104-week trial has results of clinical laboratory tests (complete blood count [CBC], blood chemistries, and urinalysis) that are clinically unacceptable to the investigator. However, it is recognized that lab results will not be available at Visit 12/12B if they occur on the same day. Therefore, such subjects may be enrolled prior to receiving these results; upon their receipt of the lab results, if the PI feels they are clinically unacceptable the subject should be discontinued.
5. Based on the results from the EOT Visit (Visit 12) has results of a physical examination, and vital signs that are clinically unacceptable to the investigator.
6. Has developed a form of dementia that is not Alzheimer's Disease, including but not limited to, dementia due to HIV infection, head trauma, vascular disease, Parkinson's disease, frontotemporal dementia, or Huntington's disease, as determined by the investigator.
7. Anticipates receiving any of the treatments listed in [Table 1](#) during the current trial.

Table 1 Prohibited Medications

Prohibited Medications, Supplements, and Other Substances
Anti-amyloid agents (e.g., tarenflurbil, tramiprosate)
Anti-amyloid antibodies (e.g., solanezumab)
Anti-amyloid vaccine (Subjects who received placebo only in a vaccine trial may participate in this trial.)

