h. Progression to dementia should be evaluated at all visits during the long term trial until the investigator or qualified designee considers the subject as having progressed to dementia (AD or non-AD). Cases of progression in this trial will not be reviewed by an adjudication committee; therefore the final decision on progression will be the opinion of the investigator or qualified designee. Note: Subjects who were confirmed to have progressed to AD dementia by the adjudication committee in the initial 104-week trial may not continue in this trial. For those subjects for whom the adjudication committee rendered a decision of non-AD dementia, the subject may continue in this trial if in the investigator’s opinion the subject did not progress to AD or non-AD dementia during the initial 104-week trial.

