#### **7.1.2.3.1 Confirmation of Progression to Probable AD Dementia**

The principal investigator or qualified designee\* will assess whether or not the subject may have progressed to dementia at all visits during the long term trial until the investigator or qualified designee considers the subject as having progressed to dementia. Cases of progression in the long term trial will not be reviewed by an adjudication committee; therefore the final decision on progression will be the opinion of the investigator or qualified designee.

**Note:** For subjects who were judged to have progressed to AD or non AD dementia by the adjudication committee in the initial 104-week trial, the investigator should document in their study records the reasons they judge that the subject had not progressed to dementia prior to the subject entering the extension trial.

\* Note: Please refer to the Manual of Assessments for qualifications required of the Qualified Designee when the Qualified Designee completes the assessment of progression to probable AD dementia.

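### Footnote h of the flow chart and the note in Section 7.1.2.3.1 give opposite entry decisions for a subject adjudicated to AD dementia whom the investigator judges not demented

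*Combined protocol and SAP*

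**What the plan says.** Three places in the protocol bear directly on a subject whom the adjudication committee of the initial trial judged to have dementia.

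- **Section 6.0, footnote h.** For an AD decision: "Subjects who were confirmed to have progressed to AD dementia by the adjudication committee in the initial 104-week trial may not continue". For the other kind of decision: "For those subjects for whom the adjudication committee rendered a decision of non-AD dementia, the subject may continue in this trial", provided the investigator holds that neither AD nor non-AD dementia had developed in the initial trial.
- **Section 7.1.2.3.1, note.** It opens "For subjects who were judged to have progressed to AD or non AD dementia by the adjudication committee" and requires the investigator to put on record the "reasons they judge that the subject had not progressed to dementia prior to the subject entering the extension trial".
- **Section 5.1.3.** Exclusion criterion 1 reads "Has progressed to dementia due to AD per investigator diagnosis in the initial 104-week study". The same sentence is printed again after Table 1 as a second item numbered 7.

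The general statements do not say whose diagnosis counts. Section 2.1 has "Subjects who progress to dementia due to AD in the main 104 week study will not be permitted to move into" the extension, Section 1.0 says the same, and Section 4.2.1.2 excludes progressors without naming who decides.

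**The concern.** Consider a subject whom the committee judged to have AD dementia and whom the investigator judges not demented. One part of the protocol turns this subject away and another assumes the subject enters.

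The exclusion is the primary reason for the amendment. The Summary of Changes explains that "the balance of benefit/risk no longer supports entry of subjects with AD dementia in the extension, where active treatment may be newly initiated". Section 4.2.1.2 adds that Protocol 017 showed more adverse events and no efficacy, and that the blind makes it impossible to admit progressors who had been on active drug while keeping out those who had been on placebo. A site that admits such a subject therefore cannot limit entry to people already on treatment, and a former placebo subject would be starting MK-8931 for the first time. A site that follows footnote h would refuse the same subject.

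**Working it through.** This is mainly a comparison of texts. The inputs are the current wording of Sections 1.0, 2.1, 4.2.1.2, 5.1.3, 6.0 (footnote h) and 7.1.2.3.1. The Summary of Changes is used only for the stated motive, not as evidence of the conflict.

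**Step 1. Apply each rule to the disputed subject** (committee: AD dementia; investigator: not demented).

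| Place | Whose judgement it uses | Result |
|---|---|---|
| 6.0, footnote h | Committee, no investigator exception | May not continue |
| 7.1.2.3.1, note | Investigator, with reasons recorded | Entry presupposed |
| 5.1.3, criterion 1 and its duplicate | Investigator; committee not mentioned | Not excluded by this criterion |
| 1.0, 2.1, 4.2.1.2 | Not named | Cannot be determined |

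**Step 2. Check how far the conflict reaches.** Change the committee's decision to non-AD dementia and keep the investigator's view. Footnote h now allows entry, the note in 7.1.2.3.1 again presupposes it, and criterion 6 of Section 5.1.3 (non-AD dementia) also rests on the investigator. The sections agree, so the conflict is confined to AD adjudications.

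**Step 3. Look for a reading that satisfies both notes.** If footnote h governs, the part of the 7.1.2.3.1 note that covers AD adjudications applies to nobody, because no such subject can enter. If the note governs, the prohibition in footnote h fails in the case where investigator and committee disagree. Reading footnote h as limited to cases the investigator had already diagnosed does not help. The protocol does not define the committee's confirmation that way, and footnote h itself foresees a committee finding of dementia where the investigator found none.

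**Step 4. Look for a rule of precedence.** None is stated for eligibility. The provision that the investigator's opinion is final concerns progression during the extension, which is not adjudicated. It does not reach committee decisions from the initial trial.

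**Step 5. What follows for each subject admitted.** Section 4.2.1.2 states that subjects "who progress to dementia during that time have a 2 out of 3 chance of being on active treatment with MK-8931". The chance of having been on placebo is then 1 − 2/3 = 1/3. The arm sizes under Table 9 in Section 8.2.11.1.2 agree: 450/1350 = 1/3. Carrying this over to the disputed subjects assumes that progression rates, and rates of disagreement between committee and investigator, are similar across arms. The documents give no disagreement rate and do not show how cases reached the committee, so no count can be derived.

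**The case against.** The strongest reply is that footnote h is a single outlier. Eligibility is set in Section 5.1.3, Section 7.1.1.2 has the investigator or a designee review those criteria, and criterion 1 names the investigator's diagnosis. Section 7.1 describes the flow chart as a summary and Section 7 as the detail. The Summary of Changes also describes the new exclusion as based on investigator diagnosis, and it lists 5.1.3 and 7.1.2.3.1 but not 6.0. It is true that criterion 1 leans towards the 7.1.2.3.1 note. But criterion 1 does not mention the committee, the wording in Section 7.1 is about procedures, and the log is not operative text. None of these withdraws an express prohibition that a site will read in the flow chart.

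A second reply is that the 7.1.2.3.1 note only imposes record-keeping and grants no permission. So the conflict is between an express bar and an implication. That is a fair description, but the implication is strong: a duty to explain why an AD-adjudicated subject had not progressed before entering has no use if that subject can never enter.

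A third reply is that the safety argument assumes the committee is right, since the investigator considers this subject not demented. This point stands. Whether admission would defeat the amendment's purpose depends on whose judgement governs, and that is what the protocol leaves open.

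Finally, the 2-in-3 figure describes progressors in general, not the subset in dispute. The 1-in-3 figure is therefore only indicative.

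**Conclusion.** The inconsistency is real and the entry rule is wrong as written. For a subject adjudicated to AD dementia whom the investigator judges not demented, the current text supports opposite entry decisions, and nothing in the protocol says which prevails. The number of subjects affected is unknown and may be small. The case for correction rests on contradictory instructions about a safety-motivated exclusion, not on a count. The about 1-in-3 chance that an admitted subject newly starts treatment is conditional on the assumptions given above. The conflict does not extend to non-AD adjudications. Which rule is right is for the sponsor to decide, and no view on that is taken here.

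**What to change.** Reconcile exclusion criterion 1 in Section 5.1.3 (and its duplicate numbered 7), footnote h in Section 6.0 and the note in Section 7.1.2.3.1. All should name the same decision-maker and the same outcome when committee and investigator disagree about AD dementia. The sponsor chooses the rule, and sites are then notified of the reconciled wording. The cost is a wording change in three sections and a site notice, with no change to the analysis.

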## **7.0 TRIAL PROCEDURES**

### **7.1 Trial Procedures**

The Trial Flow Chart - Section 6.0 summarizes the trial procedures to be performed at each visit. Individual trial procedures are described in detail below. It may be necessary to perform these procedures at unscheduled time points if deemed clinically necessary by the investigator.

Furthermore, additional evaluations/testing may be deemed necessary by the investigator and or the Sponsor for reasons related to subject safety. In some cases, such evaluation/testing may be potentially sensitive in nature (e.g., HIV, Hepatitis C, etc.), and thus local regulations may require that additional informed consent be obtained from the subject. In these cases, such evaluations/testing will be performed in accordance with those regulations.

#### **7.1.1 Administrative Procedures**

##### **7.1.1.1 Informed Consent**

The investigator or qualified designee must obtain documented consent from each potential subject or each subject's legally acceptable representative prior to participating in a clinical trial.

###### **7.1.1.1.1 General Informed Consent**

Consent must be documented by the subject's dated signature or by the subject's legally acceptable representative's dated signature on a consent form along with the dated signature of the person conducting the consent discussion.

A copy of the signed and dated consent form should be given to the subject before participation in the trial.

The initial informed consent form, any subsequent revised written informed consent form and any written information provided to the subject must receive the IRB/ERC's approval/favorable opinion in advance of use. The subject or his/her legally acceptable representative should be informed in a timely manner if new information becomes available that may be relevant to the subject's willingness to continue participation in the trial. The communication of this information will be provided and documented via a revised consent form or addendum to the original consent form that captures the subject's dated signature or by the subject's legally acceptable representative's dated signature.

Specifics about a trial and the trial population will be added to the consent form template at the protocol level.

The informed consent will adhere to IRB/ERC requirements, applicable laws and regulations and Sponsor requirements.

Given the trial population and the duration of the study, it is possible that a subject's cognition may decline to a point where they no longer have capacity to provide informed consent. If this occurs, the site should obtain consent to continue in the trial from the subject's legally acceptable representative and **in accordance with local standards and requirements**. The subject's assent to continue should also be obtained. In Germany only, due to more restrictive regulations, subjects who progress to the point where they are judged to be unable to give informed consent must be discontinued from the trial.

#### **7.1.1.2 Inclusion/Exclusion Criteria**

All inclusion and exclusion criteria will be reviewed by the investigator or qualified designee to ensure that the subject qualifies for the trial.

#### **7.1.1.3 Subject Identification Card**

In the initial 104-week trial, all subjects were given a Subject Identification Card identifying them as participants in a research trial. The card contains trial site contact information (including direct telephone numbers) to be utilized in the event of an emergency.

#### **7.1.1.4 Concomitant Medications Review**

##### **7.1.1.4.1 Concomitant Medications**

The investigator or qualified designee will record medication, if any, taken by the subject during the trial.

#### **7.1.1.5 Trial Compliance (Medication/Diet/Activity/Other)**

As part of the routine recording of the amount of trial treatment taken by each subject, the number of pills remaining in trial packaging will be counted and recorded at each regular visit. These results will be used to calculate subject compliance. Instances where the subject took more or less trial medication than prescribed will be recorded on the study medication eCRF. Events that meet criteria for overdose as defined in Section 7.2.1 will also be reported as an AE (ECI or SAE, as applicable). To monitor for potential misuse, the site will document significant discrepancies in drug returns where the subject or trial partner returns less trial medication than expected but denies taking extra trial medication (e.g., lost or missing medication equivalent to more than one pill per week).

#### **7.1.2 Clinical Procedures/Assessments**

##### **7.1.2.1 Trial Partner Attendance at Trial Visits**

The trial partner is expected to accompany the subject to all trial visits when feasible. At the discretion of the investigator, exceptions are acceptable, such as visits where no clinical measures are scheduled for administration to the trial partner. However, in these instances, the trial partner should be contacted by phone to complete AE, concomitant medication, and trial medication compliance review. For additional details, the Sponsor may be consulted.

## **7.1.2.2 Physical Assessments/Examinations**

### **7.1.2.2.1 Vital Signs**

The following vital signs will be measured and recorded: pulse (beats/minute), blood pressure (mm Hg), temperature (°C/°F), and respiratory rate (breaths per minute). Blood pressure should be measured in the sitting position.

### **7.1.2.2.2 Body Weight (kg/lbs)**

Body weight data will be collected and recorded. Body weight data will be collected without shoes and with heavy clothing removed. Body weight should be performed on the same scale for the same individual. Measurements should be recorded to the nearest kilogram/pounds.

### **7.1.2.2.3 Directed Physical and Neurological Examinations**

A routine physical and neurological examination with focus on subject-specific signs and symptoms should be performed. If the subject is discontinued for any reason during the treatment phase, every attempt should be made to perform a final physical examination.

